5.7 Dose modifications of Umbralisib and Ibrutinib for Adverse Reactions

If cytopenias are deemed related to the underlying disease rather than either umbralisib or ibrutinib, dose reductions are not required, or are per investigator discretion.

Worst CTCAE Grade Toxicity	Action to be Taken
Grade	Neutropenia Management
≤ Grade 1	No action required.
Grade 2	No action required; consider growth factor support.
Grade 3 or 4 first occurrence	Hold until < Grade 3. Consider growth factor support. Recheck in at least
	1 week. Re-challenge at same dose level.
Grade 3 or 4	Hold until < Grade 3, or at patient's previous baseline. Recheck at least
subsequent Occurrences	within 1 week. Doses are reduced 1 dose level.
Management of neutropenia is pe	er institution guidelines and if in the opinion of treating investigator, are
appropriate for patient care.	

Worst CTCAE Grade Toxicity	Action to be Taken
Grade	Thrombocytopenia Management
≤ Grade 1	No action required.
Grade 2	No action required.
Grade 3 or 4	Hold until < Grade 3, or at patient's previous baseline. Recheck at least
1 st Occurrence	within 1 week. Re-challenge at same dose level.
Grade 3 or 4 subsequent Occurrences	Hold until < Grade 3, or at patient's previous baseline. Recheck at least within 1 week. Doses are reduced 1 dose level.
Management of thrombocytopen are appropriate for patient care.	ia are per institution guidelines and if in the opinion of treating investigator,

Patients who experience an adverse event that occurs after the CTE assessment window (cycle 1-6) will be allowed to delay umbralisib or ibrutinib dosing in order to recover from the toxicity. Patients may resume umbralisib and ibrutinib, provided that the toxicity has resolved to Grade \leq 1 or baseline.

5.8 Non-Hematologic Toxicity

Grade 3 or 4 Non-Hematologic Toxicity

Worst CTCAE Grade Toxicity	Action to be Taken				
Elevated Live	r Enzymes				
Grade	Management				
≤ Grade 1	No action required.				
Grade 2	No action required.				
Grade 3 or 4	Hold until < Grade 3, or at patient's previous baseline. Recheck at least				
1st Occurrence	within 1 week. Re-challenge at same dose level.				
Grade 3 or 4	Hold until < Grade 3, or at patient's previous baseline. Recheck at least				
subsequent Occurrences	within 1 week. Doses are reduced 1 dose level.				
Management of elevated liver enzymes are at the discretion of the investigator					

The dose reduction guidelines for other Grade 3-4 non-hematologic toxicities are shown below.

NON-HEMATOLOGIC	Action to be Taken
Renal	If serum creatinine >3 x baseline or >3 x ULN, hold dose until \leq Grade 2.
Hepatic	For patients with mild liver impairment (Child-Pugh Class A) the recommended
	dose is 140mg daily (one capsule). Avoid the use of IMBRUVICA in pts with
0 1	moderate or severe hepatic impairment (Child-Pugh Class B and C).
Cardiac	If a QTcF >500 msec has been demonstrated, hold dose:
	For all patients with a new QTcF >500 msec, occurring at any time during the study as identified by the investigator, an immediate evaluation of that ECG will be obtained and confirmed.
	All cardiac events should be treated as per the local standard of care and referral to a specialist if clinically indicated. Any final decisions concerning dose modifications or permanently discontinuing the patient from study drug due to QTcF prolongation will occur after discussion between the Invest\gator.
	Atrial fibrillation and atrial flutter (range, 6 to 9%) have occurred in patients treated with IMBRUVICA, particularly in patients with cardiac risk factors, acute infections, and a previous history of atrial fibrillation. Periodically monitor patients clinically for atrial fibrillation. Patients who develop arrhythmic symptoms (e.g., palpitations, lightheadedness) or new onset dyspnea should have an ECG performed. If atrial fibrillation persists, consider the risks and benefits of IMBRUVICA treatment and dose modification

OTHER NON- HEMATOLOGIC	Recommended Action to be Taken			
Grade 1 or 2	None			
Grade 3 CTCAE	Hold dose until toxicity Grade ≤2. Reduce 1 dose level.			
If toxicity remains grade 3 toxicity for longer than 2 weeks	Reduce by one dose level or discontinue treatment			
If grade 3 toxicity lasts 2 weeks and resolves to ≤ Grade 2	Hold dose until toxicity Grade ≤2. Reduce 1 dose level			
Recurrence of Grade 3 of toxicity	Consider reducing by one dose level			
Grade 4 CTCAE	Hold dose until toxicity Grade ≤2, reduce 1 dose level.			
Recurrence of Grade 4 toxicity	Reduce by one dose level or discontinue study drug			

5.9 Dose Reduction Guidelines of Umbralisib and Ibrutinib

If a hematologic toxicity is deemed to be related to the study combination both drugs will be reduced. If a non-hematologic AE occurs and is felt to be related to only one of the study drug, this drug can be dose reduced alone.

Dose Modifications	Umbralisib	Ibrutinib	Day	Route	
-1	600 mg	560mg	Day 1-28	orally	
-2	400 mg	420mg	Day 1-28	orally	
-3	200 mg	280mg	Day 1-28	orally	

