As discussed above the phase I/lb study (NCT #02006485) with ublituximab and umbralisib in rel/ref CLL and NHL continues to accrue. An amendment to this protocol allowed for the addition of ibrutinib at 560 mg daily to UTX (fixed at 900 mg) in addition to increasing doses of umbralisib. To date, safety data on umbralisib is notable for no episodes of hepatotoxicity reported with umbralisib as a single agent or in combination with ublituximab (doublet), or with ibrutinib (triplet).(10, 16, 18) In the 12 rel/ref DLBCL patients treated with umbralisib and UTX whom were eligible for response 5 patients had obtained a response and two had a PET/CT confirmed complete responses. Sixteen patients have been enrolled into the triplet regimen without a DLT in the NHL cohorts. The 800 mg dose level of umbralisib has been enrolled and completed without a DLT. Early responses have been seen in multiple NHL subtypes.

Given the safety of the umbralisib as a single agent, in the doublet and the triplet cohorts in combination with the early efficacy signal reported we propose to further explore the safety and tolerability of an all oral regimen of ibrutinib and umbralisib in patients with rel/ref DLBCL who have relapsed post-transplant or have been determined to be ineligible or unsuitable for transplant at the full doses of umbralisib (800 mg) and Ibrutinib (560 mg) in a single center open label phase IIa study.

Section 3.0 Eligibility Criteria:

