5.2.2 Guidelines for Administration of Ibrutinib

- Method of Administration: Ibrutinib 4 capsules each 140mg = 560mg will be administered orally once daily.
 Ibrutinib should be taken in the evening. (NOTE: After cycle 2 if no CTE have been seen then the patient can have the option to take umbralisib and Ibrutinib dosing together at the same time of day).
- Ibrutinib capsules should be swallowed whole with a full glass (approximately 8 ounces) of water. Ibrutinib capsules should not be opened, chewed or dissolved.
- Potential Drug Interactions: Avoid co-administration with strong or moderate CYP3A inhibitors and consider
 alternative agents with less CYP3A inhibition. Concomitant use of strong CYP3A inhibitors which would be
 taken chronically (e.g., ritonavir, indinavir, nelfinavir, saquinavir, boceprevir, telaprevir, nefazodone) is not
 recommended. For short-term use (treatment for 7 days or less) of strong CYP3A inhibitors (e.g., antifungals

and antibiotics) consider interrupting ibrutinib therapy until the CYP3A inhibitor is no longer needed [see Drug Interactions (7.1)]. Reduce ibrutinib dose to 140 mg if a moderate CYP3A inhibitor must be used (e.g., fluconazole, darunavir, erythromycin, diltiazem, atazanavir, aprepitant, amprenavir, fosamprevir, crizotinib, imatinib, verapamil, and ciprofloxacin) [see Drug Interactions (7.1)]. Patients taking concomitant strong or moderate CYP3A inhibitors should be monitored more closely for signs of ibrutinib toxicity.

- Also avoid grapefruit and Seville oranges during treatment, as these contain moderate inhibitors of CYP3A and can alter ibrutinib pharmacokinetics.
- For patients with mild liver impairment (Child-Pugh class A), the recommended dose is 140 mg daily (one capsule). Avoid the use of ibrutinib in patients with moderate or severe hepatic impairment (Child-Pugh classes B and C) [see Use in Specific Populations (8.7) and Clinical Pharmacology (12.3)]
- Pre-medications: None

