9.2 Auditing

The UNMC Fred & Pamela Buffett Cancer Center Scientific Review Committee (SRC) will review this protocol on at least an annual basis.

This study will undergo audit on at least a quarterly basis by the UNMC Fred & Pamela Buffett Cancer Center Audit Committee.

Detailed policy and procedures for this section may be reviewed at: http://www.unmc.edu/cancercenter/clinical/prms.html.

Section 10.0 Statistical Considerations

The phase IIa portion will further assess the safety and tolerability and allow a preliminary assessment of the efficacy of the novel combination to provide background for an appropriately powered phase II study. We plan to accrue 24 patients into the phase IIa portion at a micronized dose of 800 mg of umbralisib and 560 mg of ibrutinib. The assessment of toxicity and efficacy will be performed within the entire cohort. To consecutively monitor the safety primary endpoint in the phase IIa portion, we will employ a sequential probability stopping rule for the predefined portion of cycles 1-4. This stopping rule specifies that the study will be terminated if a cumulative toxicity event (CTE) occurs in: $\geq 2/\text{first } 4$; $\geq 4/\text{first } 8$; or if more than 12 patients when the last (24th) evaluable patient has completed the trial have any CTE. This rule has the following stopping probability:

True	5%	10%	15%	20%	25%	30%	35%	40%	50%
toxicity									
rate									
Stopping prob.	0.000	0.000	0.001	0.004	0.016	0.056	0.118	0.243	0.632

A CTE is defined as:

- Grade ≥ 3 non-hematologic (attributed to either or both study drugs)
- Grade 4 hematologic toxicities (attributed to either or both drugs) defined as:
 - Grade 4 thrombocytopenia (platelets < 25 K/μL)
 - o Grade 4 neutropenia (absolute neutrophil count (ANC) < 0.5)
- Grade 3 thrombocytopenia or neutropenia that results in a > 7 day delay in either drug.
- One week or greater delay in initiating any cycle day 1 due to continued drug-related toxicity.

If a patient has progression of disease or is removed from study not related to a CTE after completion of 2 cycles but less than 4 cycles the patient's safety evaluation will be included, but noted appropriately. If less than 2 cycles than the patient will not be included and noted, but will not be replaced. The stopping rule would be appropriately adjusted if this were to occur.

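### Section 5.9 says both drugs are reduced for combination-related hematologic toxicity, but level -1 keeps ibrutinib at its 560 mg starting dose, and no first dose is named for an ibrutinib-only reduction

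*Combined protocol and SAP*

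**What the plan says.** **Starting doses.** Section 5.2.1 starts umbralisib at 800 mg daily. For ibrutinib, 5.2.2 says "Ibrutinib 4 capsules each 140mg = 560mg will be administered orally once daily". The combination rationale in 2.3 places the trial "at the full doses of umbralisib (800 mg) and Ibrutinib (560 mg) in a single center open label phase IIa study", and Section 10.0 plans accrual of 24 patients "at a micronized dose of 800 mg of umbralisib and 560 mg of ibrutinib".

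**Reduction rule.** Section 5.9 has two sentences and a table. The first sentence is "If a hematologic toxicity is deemed to be related to the study combination both drugs will be reduced". The second covers a non-hematologic event that "is felt to be related to only one of the study drug, this drug can be dose reduced alone". The table gives three levels (umbralisib / ibrutinib): -1 is 600 / 560 mg, -2 is 400 / 420 mg, -3 is 200 / 280 mg.

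**Triggers.** In 5.7, a first grade 3-4 neutropenia leads to a dose hold ("Hold until < Grade 3. Consider growth factor support") and then "Re-challenge at same dose level". A first grade 3-4 thrombocytopenia is handled in the same way, without the growth-factor advice. For later occurrences of either, after a hold, "Doses are reduced 1 dose level". In 5.8, other grade 3 and grade 4 non-hematologic events call for a hold until grade 2 or lower and then a one-level reduction.

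**Discretion.** The last paragraph of 5.6.1, just before 5.6.2, calls these steps recommendations. It leaves the choice of drug, the actual reduction and the number of reductions to the treating investigator.

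**The concern.** The first sentence of 5.9 and the first row of its table cannot both be followed. An investigator who applies the sentence lowers both drugs. An investigator who applies the one-level step from the table lowers umbralisib and restarts ibrutinib at full dose.

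The second sentence has a related gap. It permits an ibrutinib-only reduction but names no dose for it. Under the table, one level down for ibrutinib is the dose the patient was already taking.

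The primary objective is safety and tolerability, and Section 2.4 justifies the design by toxicity that accumulates over later cycles. Dose reductions are part of how tolerability is managed and reported, so a one-level reduction should have a single meaning for each drug.

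**Working it through.** The plan states no figure that depends on this point, so there is none to reproduce. The check compares the starting doses (5.2.1, 5.2.2) with each row of the 5.9 table.

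**1. Size of each step.** Reduction = 1 - (level dose / starting dose).

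| Level | Umbralisib | Ibrutinib |
|---|---|---|
| -1 | 1 - 600/800 = 25% | 1 - 560/560 = 0% |
| -2 | 1 - 400/800 = 50% | 1 - 420/560 = 25% |
| -3 | 1 - 200/800 = 75% | 1 - 280/560 = 50% |

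The rows are complete and evenly spaced: umbralisib falls by 200 mg per level, and ibrutinib by 140 mg per level from -1 downward. Nothing suggests that the 560 mg entry is a text-extraction fault.

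**2. Repeated events of one cytopenia type.** This applies 5.7 literally, for toxicity attributed to the combination.

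| Grade 3-4 event | Rule in 5.7 | Restart dose, umbralisib / ibrutinib |
|---|---|---|
| First | same dose | 800 / 560 mg |
| Second | down one level, to -1 | 600 / 560 mg |
| Third | down one level, to -2 | 400 / 420 mg |

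Ibrutinib first falls at level -2. That takes one event with no step plus two one-level steps: 1 + 2 = third event.

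**3. Both cytopenia types.** The protocol does not say how neutropenia and thrombocytopenia combine. Assume that first occurrences are counted separately by type and that both types move the patient down one shared ladder.

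- If the first three events are of the same type, ibrutinib falls at the third event, as above.
- If both types appear among the first three events, two events are first occurrences with no step, and two steps are still needed: 2 + 2 = fourth event.

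Under this assumption the answer is the third or fourth event, depending on order.

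**4. Ibrutinib-only reduction.** The literal one-level step is 560 - 560 = 0 mg. The first lower entry in the ibrutinib column is 420 mg (560 - 140), and the next is 280 mg.

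**5. Does another rule fill the gap?** Ibrutinib 140 mg appears for mild hepatic impairment, Child-Pugh A (5.2.2, 5.8), and for use with a moderate CYP3A inhibitor (5.2.2, Appendix A). These are separate dose settings with their own triggers. They do not define a first reduction for toxicity.

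**6. Number of patients.** Section 8.5 gives grade 3-4 neutropenia in 19 to 29% and thrombocytopenia in 5 to 17% of ibrutinib-treated patients. These are not rates for this doublet, nor rates of recurrence or dose reduction, so no count of affected patients follows from them.

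**The case against.** The strongest reply is the discretion clause in 5.6.1. It covers the drug, the dose and the number of reductions, so 420 mg is already allowed at any point. It also means that two investigators may restart similar patients at different doses, with or without a correction. Both statements are true. The fix makes the default clear but does not standardise dosing. Even so, freedom to depart from a recommendation does not settle what the recommendation is, and here its two halves disagree.

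Second, the staggered ladder may be intended, with umbralisib lowered first. That is a legitimate choice, and nothing in the documents shows otherwise. If it is intended, the sentence is what is wrong, and the doses can stay.

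Third, an ibrutinib-only step of 0 mg is a strained reading, because a reader told to reduce the drug would probably go to 420 mg. That is likely in practice, but the text leaves it to inference.

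A reader might infer that patients with ibrutinib toxicity will be put back on full dose unprotected. The documents do not support that: dosing is held first, 5.6.2 sets recovery conditions for continuing after a cumulative toxicity event (CTE), and the investigator can reduce further.

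A reader might also infer that the trial's operating characteristics are compromised. They are not. The reduction ladder enters neither the sample size of 24 nor the two-stage response design. A patient with a drug-related grade 4 neutropenia or thrombocytopenia, or a drug-related grade 3 or higher non-hematologic event, in cycles 1 to 4 already counts as a CTE when the restart dose is chosen. The restart dose could matter to the CTE count only for triggers that are not yet CTEs, such as a grade 3 cytopenia without a delay of more than 7 days. The documents give no rate for those.

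**Conclusion.** The point holds as a modest safety and coherence correction. As written, the first one-level reduction lowers umbralisib by 25% and ibrutinib by 0%, against a sentence saying that both fall. The default ibrutinib-only reduction read from the table is 0 mg. For repeated grade 3-4 events of one cytopenia type, ibrutinib first falls at the third event. With both types it is the third or fourth, on the assumption of separate counting on a shared ladder.

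These results rest on reading the sentence, the table and the one-level steps literally, starting from 800 / 560 mg. No number of affected patients is claimed. Sample size and error rates are unaffected.

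**What to change.** Keep the table and change the wording of 5.9 in two places.

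1. Replace the first sentence with one saying that, for hematologic toxicity related to the combination, level -1 reduces umbralisib only and levels -2 and -3 reduce both drugs.
2. Add that, for a patient taking ibrutinib 560 mg, an ibrutinib-only reduction goes first to 420 mg and then to 280 mg. State that patients already on 140 mg for Child-Pugh A impairment or a moderate CYP3A inhibitor are not covered by these steps; for them, 420 mg would be an increase.

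The discretion clause in 5.6.1 can stay. The cost is a wording amendment. No table dose changes, and no statistical quantity has to be recalculated. The clinical team should confirm that the staggered ladder is what was intended.

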5.10 Assessments

5.10.1 Disease Assessment Schedule

A dedicated PET/CT Response assessment will be done after cycles 2, 4, 6, 9, and 12 (+/- 7 days). After Month 12, efficacy assessments should occur at the investigators discretion. If a PET/CT CR (Deauville 3 or less) is seen then a CT of chest, abdomen, and pelvis with contrast can be substituted.

A restaging bone marrow biopsy may be done if a staging bone marrow biopsy was previously positive or if symptoms suggest involvement.

Patients with stable disease after 6 cycles can continue treatment if the treating investigator feels the subject is deriving benefit. Patients with progressive disease (PD) at any time are off study and will discontinue study treatment.

Patients achieving PR/CR or stable disease that are felt by the investigator to be deriving a benefit may continue until disease progression or for a maximum of 12 cycles (52 weeks of any treatment).

5.10.2 Post Trial Assessments

Patients who go off study treatment at any time during the trial will be followed for 30 days after the last day of treatment. For all patients, drug-related SAEs and AEs will be followed until baseline or ≤ grade 1 levels. Patients who responded or maintained stable disease during the study will be followed for date of disease progression. Patients may refuse to participate in the post-trial assessments.

5.11 Biospecimens

5.11.1 Mandatory Human Biologic Materials

Pathology materials should be submitted and reviewed at UNMC confirming the diagnosis of DLBCL or transformed DLBCL.

Mandatory peripheral blood (20 mL) for cell free DNA assessment and peripheral mononuclear cells will be collected in an EDTA tube pretreatment (day of biopsy or initiation of treatment), day 8, 1 month (+/- 3 days) and 10 mL will be collected at subsequent radiographic response assessments, after cycle 2, 4, 6, 9, and 12. (+/- 7 days). After Month 12, efficacy assessments should occur at the investigators discretion with collection of a research blood sample only if feasible.

5.11.2 Somatic Mutations Affecting B-cell Receptor Signaling

Prior studies have identified somatic mutations in genes that regulate or modify signaling downstream from the B-cell receptor and toll-like receptor pathway, including CD79A, CD79B, CARD11, and MYD88. In addition, these mutations may be associated with the clinical response to Ibrutinib. To account for the potential influence of these mutations on response, they will be assessed from pre-treatment biopsy specimens by next generation sequencing. To achieve this, DNA will be extracted from tumor specimens, genome-wide next generation sequencing libraries constructed, and hybrid capture utilized to isolate 386 genes that are recurrently mutated in B-cell lymphoma, including those listed above.

5.11.3 Quantitative Assessment of Kinetics and Depth of Response

Tumor cells release DNA into the peripheral blood and it is detectable within the cell-free DNA (cfDNA) fraction isolated from plasma. Recent studies have shown that the burden of tumor specific cfDNA in the plasma correlates with metabolic tumor volume.(19, 20) In order to quantitatively assess the magnitude and kinetics of response and association with radiographic response we will employ cfDNA sequencing by isolating cfDNA from peripheral blood samples collected in a 20 ml EDTA tube pretreatment (day of biopsy or initiation of treatment), day 8, 1 month (+/- 3 days) and 10mL EDTA tube at subsequent radiographic response assessments, after cycle 2, 4, 6, 9, and 12. (+/- 7 days). After Month 12, efficacy assessments should occur at the investigators discretion with 10ml EDTA peripheral blood samples obtained ONLY IF FEASIBLE. We will create next-generation sequencing libraries, and performing hybrid capture for genes with identified mutations from the tumor biopsy specimen as well as immunoglobulin genes. (Appendix G Blood and Tissue Sample Processing and Shipping)

This will allow multiple tumor-specific genetic markers to be followed in the peripheral blood, and quantitative assessment of response to be calculated by the change in allelic fraction of somatic mutations.

5.11.4 Cell Signaling Characteristics

Malignant B-cells have unique intracellular signaling characteristics that vary between patients.(21) We will assess the basal level of signaling downstream from the B-cell receptor in pre-treatment biopsies using intracellular phosphospecific flow cytometry. Therein, tumor B-cells can be identified using surface markers and fixed and permeabilized cells interrogated using antibodies that are specific for activating phosphorylation markers on multiple proteins. Using fluorescent barcoding and 10-color multiplexing, we will assess the activity of proximal B-cell receptor signaling components (Lyn, Syk, Btk, Blnk, Plcg2), phosphoinositol-3-kinase signaling molecules (Akt, S6K) and downstream targets of casein kinase signaling (EIF4E, Myc)). This will provide a quantitative measure of the basal activation of these pathways within patient tumor biopsies prior to treatment. Optional lymph node biopsies will be obtained via US or computer tomography (CT) guided biopsy of accessible lymph nodes at day 0 (pre-treatment; core biopsy), day 8 (FNA) and end of treatment (progressive disease, toxicity, or end of study—1 year; core biopsy) so as to assess the change in signaling resulting from treatment. (Appendix G Blood and Tissue Sample Processing and Shipping)

